Height (measured)		X	X	X
Waist (measured)		X	X	X
BP (measured)		X	X	X

Patterned after protocol published online in association with Appel et al. (2011)¹⁵

Randomization		X		
Questionnaire topics (administered in this order)				
Demographics/Medical	X	X		X
WHO Health and performance questionnaire		X	X	X
Health-Related QoL-SF-12		X	X	X
Mental Health Inventory (MHI-5)		X	X	X
Physical Activity Quest. (IPAQ)		X	X	X
Physical Activity self-efficacy		X	X	X
Outcomes: hunger – fullness - satisfaction		X	X	X
MyPlate adherence		X	X	X
MyPlate self-efficacy		X	X	X
Weight loss history		X	X	X
Weight control self-efficacy (WEL-SF)		X	X	X
Patient sense of autonomy		X	X	X
Patient satisfaction with care			X	X
Social support and eating habits survey		X	X	X
Social support and exercise survey		X	X	X
TV/Monitor use time		X	X	X
USDA Short-Form Food Security survey		X	X	X
Medical History survey			X	X
Patient satisfaction with weight loss program			X	X
Block Food Freq. Quest.		X		X

*note. F-up-6 = follow-up assessment 6 months after randomization; F-up-12 =follow-up assessment 12 months after randomization.

Principal Measures

The following sections describe the specific measurements to be collected from participants at each contact point in the trial. After considering the total burden of data collection procedures and measurements, we may drop or modify some items. We may also add questionnaires. For example, to improve study procedures and interventions, we will query participants about their experiences in the study.

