We also plan to gauge patients' patient activation **sense of autonomy** in medical decision-making occurring during the visit, drawing on recent work^{131,132} for measuring both patient perception of the actual autonomy that they experienced during the visit and the amount of autonomy they wanted to experience. We will explore the use of the stem question – "When considering ways to lose weight, please think about who should make the decision, your doctor or yourself? Please select which of these statements is most appropriate for you: Considering your visit today (or last visit): (1) who made the decisions about your care?" (doctor or patient); and (2) "Who **should** have made the decisions about your care?" (doctor or patient)."

We plan to administer the SF-12, an abbreviated **health-related quality of life** instrument, based on the SF-36.¹³³ Test-retest (2-week) correlations of 0.89 and 0.76 were observed for the 12-item Physical Component Summary and the 12-item Mental Component Summary, respectively, in the general US population (n = 232).¹³³ A Spanish translation of this instrument is available and has similar psychometric properties.^{134,135} Our **patient satisfaction with their weight loss program** is adapted from literature evaluating consumer satisfaction with consumer products.¹³⁶ As part of a set of post-intervention evaluation questions concerning patient judgments about intervention components the question was asked: "Would you recommend this Program to your family members or friends?" Answer options included: "Yes, definitely," " Maybe," and "No." In evaluating business products, this single item has been unusually effective in discriminating high consumer satisfaction with products from less successful products.¹³⁶

We will test the reliability of these scales for our minority clinic populations and evaluate the meaning of these items when translated into Spanish, during cognitive testing prior to study implementation.

Secondary patient medical outcomes include: BMI, waist circumference, and blood pressure.

Height (cm) to the nearest 0.1 cm will be measured once at entry using a calibrated, wall-mounted stadiometer in the clinic. The participant stands shoeless on a level surface, with his/her head in the horizontal (Frankfort) plane.

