Waist Circumference (cm) will be measured by trained staff using an anthropometric measuring tape (Gulick anthropometric), at a horizontal plane around the abdomen just above the uppermost lateral border of the right iliac crest (i.e. the top of the hip bone).¹³⁷ Obesity cutpoints of 88 cm (women) and 102 cm (men)¹³⁷ will be used in analyses. Because visceral fat expresses inflammatory cytokines that increase cardiovascular risk,¹³⁸ waist circumference is arguably more predictive of future heart disease than overall obesity.¹³⁹

For the waist circumference measurement, the subject should be wearing a top and short, pants, or skirt, adjusted to obtain access to the waistline. If it is not possible to access the waistline, the measurement can be taken over thin clothing (thin shirt or blouse), and this should be noted on the data entry form. The participant should stand with abdomen relaxed, arms at sides, and feet close together with weight equally distributed between both legs.

Participant's preference of Research Assistant's gender taking waist circumference should be taken into consideration prior to taking measurement. In addition Research Assistant (RA) should ask patient if they feel more comfortable having the measurement taken under or over clothing. RAs will ask patients:

"The next measurement is your waist circumference. This measurement is more accurate if we measure it under clothes and directly on top of the skin. Would it be OK if we measure your waist circumference under your clothes? Or do you prefer over your clothes?"

Patterned after protocol published online in association with Appel et al. (2011)¹⁵

Analytically, the bias introduced by measurements over clothing instead of against the skin- which is ideally the way waist circumference should be measured- can be corrected for by subtracting the mean increase in waist circumference associated with measuring the waist circumference over clothing compared to waist circumference associated with measuring the waist circumference over skin.¹⁴⁰

BMI will be calculated as the Quetelet index (kg/m²). Although BMI is collinear with body weight, it is included in order to provide comparability with other studies, where BMI was the primary outcome.

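### Waist may be taken over or under clothing with no rule to keep the mode constant across visits, and the text and Table 4 disagree on whether height is re-measured; both add avoidable error to secondary change outcomes.

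*Combined protocol and SAP*

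**What the plan says.** All of the measurement text is in Section 8.

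- **Waist, access rule.** "If it is not possible to access the waistline, the measurement can be taken over thin clothing (thin shirt or blouse), and this should be" (the sentence closes by requiring that staff mark this on the form).
- **Waist, preference rule.** The research assistant "should ask patient if they feel more comfortable having the measurement taken under or over clothing", and the script, after saying that skin measurement is more accurate, asks: "Would it be OK if we measure your waist circumference under your clothes? Or do you prefer over your clothes".
- **Waist, correction.** The over-clothing bias "can be corrected for by subtracting the mean increase in waist circumference associated with measuring the waist circumference over clothing" relative to skin. A source is cited, but no value is given and no rule for applying it. Section 14 (Analysis Plan) does not mention it.
- **Waist, schedule.** The Table 4 row beginning "Waist (measured" is marked at baseline, 6 and 12 months.
- **Height.** The Height paragraph says that it "will be measured once at entry using a calibrated, wall-mounted stadiometer in the clinic". The Table 4 row beginning "Height (measured" is marked at baseline, 6 and 12 months.
- **BMI.** It is defined as the Quetelet index, without saying which height is used at follow-up.
- **Blood pressure, for contrast.** The cuff size chosen at the first visit is kept for all later visits.

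Section 8 lists BMI and waist as secondary medical outcomes. Section 2 names reduction in waist as a primary medical outcome alongside weight. The Abstract's secondary hypotheses expect significant and similar declines in weight and waist in both conditions.

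**The concern.** A change score is clean only if both readings are taken in the same way. Here the clothing mode can follow the participant's preference on the day. Someone measured over clothing at baseline and on skin at 12 months shows a reduction that is partly fabric. Such a move is plausible in people who have lost weight, though nothing in the documents demonstrates it.

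The hypothesis most exposed is the decline within each arm, because randomisation does not protect a before-after comparison. The correction described could remove the average shift, but only if the mode is known for every reading. The explicit instruction to note it covers inaccessible waistlines and is not repeated for over-clothing by preference.

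The height conflict leaves staff without a clear instruction and the analyst without a defined BMI. If follow-up heights are taken and used, height measurement error enters the BMI change.

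**Working it through.** The plan states no sample size, power or clothing offset for waist or BMI, so there is no figure to reproduce. The sums below only indicate size.

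**Inputs.** From the documents: N = 261, and 20% expected attrition (given for 6 months in Section 13). Assumed, because the documents give nothing: clothing offset c = 0.5-3 cm; fall in the share measured over clothing of 0-30 percentage points; SD of waist change 6-8 cm; height error e = 0.5-2 cm; illustrative participant at 160 cm with BMI 33.

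**1. Spurious within-arm mean change, uncorrected.** c × (share over clothing at follow-up − share at baseline).
- Stable share: 0.
- Smallest non-zero case: 0.5 × (−0.10) = −0.05 cm.
- Middle case: 2 × (−0.20) = −0.4 cm.
- Largest case: 3 × (−0.30) = −0.9 cm.

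For scale, 261 × 0.80 ≈ 209, or about 104 per arm. The standard error of a within-arm mean change is then 6/√104 ≈ 0.59 cm to 8/√104 ≈ 0.78 cm. Only the upper corner of the assumed range reaches one standard error.

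**2. Added noise.** If each participant chose independently and 50/50 at two visits, the variance added to the change is c² × (0.25 + 0.25) = 0.5c².
- c = 1 cm: 0.5 cm²; 0.5/64 ≈ 0.8% at SD 8, and 0.5/36 ≈ 1.4% at SD 6.
- c = 3 cm: 4.5 cm²; 4.5/64 ≈ 7.0% at SD 8, and 4.5/36 = 12.5% at SD 6.

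**3. Bias between arms, if it existed.** Suppose over-to-under switching were 10 points more common in one arm (assumed) and c = 1-3 cm. The bias is 0.1-0.3 cm uncorrected, or 0.05-0.15 cm if a correction were applied with an offset 50% wrong. The standard error of the arm difference is 6 × √(2/104) ≈ 0.83 cm to 8 × √(2/104) ≈ 1.11 cm. So 0.15/0.83 ≈ 0.18, about one fifth of a standard error at most after such a correction.

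**4. BMI with re-measured height.** The spurious individual change is BMI × [(h/(h − e))² − 1]. At h = 160 cm and BMI 33:
- e = 0.5 cm: 0.21 kg/m².
- e = 1 cm: 0.42 kg/m².
- e = 2 cm: 0.84 kg/m².

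A true 2 kg weight change at that height is 2/1.60² = 0.78 kg/m². These are errors for one person. Random height error averages out of the group mean, and the term is zero if one baseline height is used throughout.

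**The case against.** The strongest reply is that the plan already sees the problem. It names the over-clothing bias, tells participants that skin measurement is more accurate, and describes a correction. Where a participant's mode does not change, the average offset cancels in the change score, so the correction has nothing to do there and that is no defect. Where the mode does change, correcting the average is most of what a comparison of means needs. Follow-up data collectors are masked (Section 10), the weight outcome is untouched, BMI is reported only for comparability with other studies, and Section 9 promises a fieldwork manual that may hold the missing rule and is not available here.

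Most of this stands, and it limits the point to a minor one. It does not close the gap. The correction is worded as a possibility, has no value, is missing from the analysis plan, and depends on a mode whose recording is not clearly required.

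Four stronger readings are tempting and not supported.

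- **The question is asked at every visit.** The text does not say so. It is a reasonable inference from the script and the Table 4 schedule.
- **The arm comparison is biased.** That needs switching to differ by arm. Participants are unmasked, so it is possible, but the Abstract expects similar declines in both arms, so switching driven by weight loss would be roughly balanced on the plan's own expectation.
- **The correction imports an external offset.** A source is cited, but the text does not say where the value will come from.
- **Mean BMI change is biased.** No text says that follow-up heights enter BMI, and random height error would not shift the mean.

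**Conclusion.** The point holds as a minor one. No stated rule keeps the waist mode the same across visits, mode recording is explicit for only one of the two routes to an over-clothing reading, and the correction is left undefined. The consequence is added noise in waist change (about 1%-13% of its variance if choices are independent and 50/50, with c = 1-3 cm and SD 6-8 cm) and a possible spurious within-arm decline of 0.05-0.9 cm before any correction, or none if over-clothing use is stable. All of these sizes rest on assumed offsets, switching rates and SDs.

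The height conflict between the text and Table 4 is a plain inconsistency. Its effect is individual-level noise in BMI change, and only if re-measured heights are used.

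A reader might infer that the comparison of MyP with CC on waist is compromised. The documents do not show that, and on the assumptions above the effect would be a fraction of a standard error. Weight is unaffected, and no sample size or power figure in the plan changes.

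**What to change.** - Record the clothing mode at every waist measurement, whatever the reason for it.
- At 6 and 12 months, repeat the baseline mode where the participant agrees.
- Where the mode differs, record the switch and, if the participant agrees, take both readings at that visit so that the offset can be estimated from trial data.
- In Section 14, state the offset, its source and when it is applied, and add a sensitivity analysis limited to participants with the same mode at both visits. The offset rule is still needed for the 88 and 102 cm waist cutpoints, because a constant mode does not correct a single reading.
- Compute BMI at every visit from the baseline height, and reconcile the height row of Table 4 with the Height paragraph.

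The cost is a few lines in the fieldwork manual and the analysis plan, and a second tape reading for those who switch. There is a real downside: some participants stay in the less accurate over-clothing mode, and the offset then cancels only approximately, because garments vary between visits. If data have already been collected, the height rule can still be set, and so can the same-mode sensitivity analysis wherever the mode was recorded.

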9. QUALITY ASSURANCE AND QUALITY CONTROL

Quality Assurance (QA) pertains to activities that promote collection of high quality data, while Quality Control (QC) pertains to activities that detect emerging issues. Our basic approach to QA is as follows:

- prepare a well-documented fieldwork manual of procedures,
- implement a trainer model to train and certify other staff
- train and certify all primary data collectors, with special emphasis on procedures related to trial outcomes,
- establish proficiency requirements before initial certification of data collectors,

Patterned after protocol published online in association with Appel et al. (2011)¹⁵

- routinely observe data collectors,
- routinely calibrate equipment, including weekly calibration of the weight scales used for assessing body weight and regular calibration of the blood pressure equipment
- use cognitive testing to ensure that Spanish translations of questionnaires are comparable in meaning to the English versions; use cognitive testing to ensure that new and other conceptual questions measure what they were intended to measure
- pilot test new questionnaires and data collection procedures
- maintain logs of certified data collection staff and calibrated equipment.

To identify problems with sufficient time to institute appropriate corrective actions and to quantify the quality of data collected during the trial, we will perform the following QC activities:

- monitor counts of completed assessments and key data collection items,
- monitor distributions of trial outcomes, overall, by data collector,
- issue queries about missing data, out of range values, or illogical data relations,
- review types and distribution of data entry errors.

10. RANDOMIZATION AND MASKING

Randomization

Randomization. As mentioned above in describing the use of REDCap in recruitment, if all measures indicate that the patient remains eligible, a programmed application in REDCap will generate a random assignment to experimental condition for the patient at the end of the screening assessment. The lifestyle change coaches can look up in REDCap's database the study participants assigned to their condition. The coach will then call the patient and arrange for the first coaching session, if appropriate. The research assistants will be kept ignorant of the patient's assignment to experimental condition, to reduce the chance for bias. Of necessity, the behavior change / lifestyle change coaches will be aware of the patient's experimental assignment but will be instructed to follow the protocol carefully, so as not to introduce any personal bias.

Masking

Trial participants will know their intervention assignments, as will the community health worker staff that are involved in delivering the interventions. However, UCLA fieldwork staff involved in follow-up data collection will be kept masked to participants' randomization assignments.. At the conclusion of the trial, participants will receive a summary of clinically relevant measurements. .

11. INTERVENTIONS

Overview of the interventions. The MyP and CC interventions to be tested here are evidence-based lifestyle counseling programs that have been adapted from those implemented in other weight loss trials.^{14,15} Other trials that have informed the design of our interventions include the Diabetes Prevention Program and LookAhead.^{86,148} Although not weight loss trials, the DASH trials (DASH, DASH-Sodium and OmniHeart) helped to provide the scientific rationale for the dietary advice to be offered to achieve and maintain desirable weight loss.^{17,149-151} Both the MyP and CC interventions seek to generate a daily energy deficit as long as the participant has excess weight to lose. Both interventions limit intake of high energy foods and both encourage increasing expenditure of energy in daily physical activity. Both interventions use standard cognitive behavioral approaches to behavior modification, including self-monitoring of behavior, relapse prevention, and mobilizing social support for sustaining adherence to the recommended lifestyle approach. The MyPlate/DASH-style intervention differs from the CC approach principally by its insistence that the form of the food in which calories come can influence

metabolic functioning and appetite and can make a difference to quality of life, to optimal nutritional health, and to the sustainability of the weight loss approach for a lifetime. The CC approach, by contrast, asserts that a calorie is a calorie and that it does not matter whether the calories come from minimally processed fruits and vegetables or from highly processed juices derived from fruits and vegetables. The DASH-style approach therefore limits intake of juices and limits the consumption of highly processed carbohydrate-rich foods including ready to eat breakfast cereals, refined wheat breads, pizza, chips, pastries, candies, power bars and fruit smoothies. As previously noted, the DASH-style approach also strongly encourages increasing the intake of fresh fruit and vegetables to at least twice the daily intake of the average American adult, as well as increased intake of whole grain cereals, legumes, seeds and nuts.

Theoretical Rationale/ Model Underlying the Interventions

The theoretical framework for the CC and MyP interventions draws largely upon the strengths of behavior changes theories, specifically, social cognitive theory,^{34,152} Behavioral self-management and motivational enhancement^{153,154} approaches are used as a foundation to teach participants strategies including goal setting, self-monitoring, problem solving and identification of barriers and strategies for overcoming these barriers. Both interventions are designed to promote weight control self-efficacy and to help participants identify and develop sources of social support. Both self-efficacy and social support are key components in social cognitive theory and have been identified as important determinants of behavior change.³⁴ These efforts will work in conjunction with behavior change counseling in the primary care setting. U.S. Preventive Services Task Force (USPSTF) has recommended this multi channel approach to promoting lifestyle change.^{103,155} One feature that distinguishes the CC and MyP theoretically is the emphasis that the MyP approach places on environmental cues to support the recommended behavior changes initially achieved through goal-setting, self-management and motivational enhancement. This emphasis on the importance of the physical environment is more in keeping with Social Ecological Theory¹⁵⁶ than Social Learning theory.³² Social ecological models of health promotion identify several levels of environmental influence on diet and physical activity, ranging from familial to global factors. At the most proximal level, there is increasing evidence that the home micro-environment can be obesogenic. Both physical (e.g., type of food available) and social (e.g., support from family) factors in this setting have been associated with weight, dietary habits, and activity patterns.^{47,48} Demonstrated links between the physical home environment and behavior include relationships between available high-fat foods and fat intake,⁴⁹ access to home exercise equipment and activity levels,^{50,51} and number of televisions and amount of television viewing.⁵²

The utility of the calorie-counting (CC) approach to energy restriction was predicated on the assumption that a calorie is a calorie, no matter what its source, and that weight loss could be achieved regardless of where the calories were coming from, as long as calorie expenditure exceeded calorie intake. It is a simple matter of physics. To generate a chronic calorie deficit the patient either had to increase energy expenditure, through physical activity usually, or restrict their calorie intake to a level below the level of calories expended through daily metabolism and physical activity. The behavioral theory behind the DPP calorie-counting approach views participants as active problem solvers who are capable of regulating their affect, behavior, and cognition.¹⁵⁷ Self-monitoring is used to identify times, places, emotions, people, and events associated with eating (or exercising) appropriately or inappropriately. Goal setting is facilitated by specifying behaviors to be adapted and when, where, how, and with whom they will be performed. Behavior change is reinforced by increased self-efficacy, by the inherent rewards in reaching a goal (i.e., weight loss or improved fitness), by social support (including encouragement from medical personnel) or by the use of external rewards. The provision of

long-term treatment recognizes that obesity, for most individuals, is a chronic condition that requires long-term care. The delivery of the calorie-counting intervention in primary care practice is guided by Wagner's Chronic Care Model.^{158,159} Using a community health worker lifestyle coaching approach, obese participants will be provided an evidence-based intervention (i.e., the Diabetes Prevention Program) that primary care providers can refer their obese patients to for obesity treatment. Community health worker lifestyle change coaches will be trained to guide and support participants' efforts to improve their eating behavior and physical activity using the DPP approach.

The utility of the DASH-style approach to energy restriction in MyP is predicated on helping the participant reach satiation / satiety sooner with fewer calories by careful choice of foods to consume.¹⁵¹ Feeling full with fewer calories is possible by replacing highly processed, usually energy dense and nutrient poor food choices with minimally processed foods of Mother Nature, particularly fresh fruits and vegetables. Canned fruits and vegetables are typically processed foods, high in added sodium and often high in added sugar as well, and are therefore to be consumed only in limited quantities. Participants in the MyP condition are particularly encouraged to limit most caloric beverages, including: juices, juice drinks, sugar sweetened beverages and alcoholic beverages – because of the high potential for passive overconsumption of calories from these sources.¹⁶⁰ There are several important but addressable challenges to the DASH-style approach that can benefit from systematic tracking and encouragement by a lifestyle change coach. These challenges include: 1) the neophobic response of the human palate to the taste of botanically distinct new plant foods,⁶¹ 2) the phenomenon of sensory-specific satiety,¹⁶¹ whereby appetite for a specific food declines with every additional bite of the food, 3) the negative impact that fasting has on receptivity to low-calorie, high-fiber foods,¹⁶² 4) the prerequisite importance of physical activity for generating optimal appetite for water-rich foods, specifically fruits and vegetables.¹⁶³ With supportive coaching and collaborative coach/participant problem-solving, these challenges can be overcome.

Description of Intervention Health Education / Coaching Sessions.

For the 3-months pilot study, for both interventions there will be weekly meetings of the CHW with the participant throughout, including 2 one-hour group education sessions, 2 thirty-minute in-home visits and 8 (later reduced to 7 following stakeholder input) twenty-minute telephone coaching sessions.

For the 12-months full study, for both interventions, patients will be encouraged to complete four meetings each month with their CHW so that the intervention can be completed in three months. However, if patients are unable to complete the health education lessons within this timeline, they will be allowed to complete as many lessons out of the 11 possible before their final follow-up assessment. The meetings will include 2 group education sessions during months, 2 in-home visits during months, and 7 telephone coaching sessions that taper off in frequency during the first three months of the 12-months study period. For this study, the health sessions were delivered in the following order in as described below in Table 5.

Table 5. Order and Distribution of In-Home Health Education Sessions, telephone coaching sessions, and group education sessions.

- | |
|--|
| 1) In-home health education session #1 |
| 2) Telephone coaching session #1 |
| 3) Group education session #1 |
| 4) Telephone coaching session #2 |
| 5) Telephone coaching session #3 |
| 6) Telephone coaching session #4 |

Patterned after protocol published online in association with Appel et al. (2011)¹⁵

- 7) In-home health education session #2
- 8) Telephone coaching session #5
- 9) Group education session #2
- 10) Telephone coaching session #6
- 11) Telephone coaching session #7

The TCC community health workers responsible for the lifestyle change coaching sessions will be recruited from the local community and local colleges. They will be trained and supervised by the TCC health education department, who has years of experience supervising community health workers, including community health workers making home visits. Both the community health workers and the patients will be likely to view the in-home visits as part of routine TCC care because of TCC's previous history of community health worker lifestyle change coaching.

The budget includes the telephone lines for the community health workers, to facilitate their telephone and in-home visits with study participants. The budget also includes the cost of mileage incurred while making in-home visits. Because many patients may be prevented from attending the group health education because of the cost of transportation to the group education event or the cost of childcare, each participant attending the health education will receive \$10 towards deferring the transportation cost and the participant's infant children will be provided free child care. The group education will be open to participation by family members, including spouses and children old enough to benefit from the education.

The Calorie-Counting (CC) Lifestyle Coaching Intervention Approach, as adapted by Wadden et al. (2011) from the Diabetes Prevention Program (DPP-like)

CC Behavior Change Goals. The goals of this intervention are to induce a loss of 5% or more of initial weight through energy restriction by counting calories, limiting daily intake to prescribed amounts and increasing participants' physical activity to > 150 minutes per week and to maintain these improvements over 12 months. These goals will be achieved by providing participants a program of lifestyle modification, delivered by a community health worker lifestyle coach, with encouragement from the patient's primary care provider (PCP).

Description and delivery of the CC intervention. Participants in this group will meet with their PCPs on the same schedule as those in the MyP group and receive the same attention for their comorbid conditions, as well as the weight management handouts. Participants in this condition will receive a program of lifestyle modification based on the curriculum used in the Diabetes Prevention Program (DPP). The lifestyle modification program will be delivered to participants during regularly scheduled phone calls conducted by community health worker lifestyle change coaches. We elected to use the DPP materials because they have been shown to be effective across a wide range of participants and provide tailored dietary menus for African Americans and other ethnic minorities. The DPP materials have been adapted for delivery in primary care practice by community health worker lifestyle change coaches and have obtained a loss of approximately 3.8% of initial weight during 6 months of treatment.¹⁴

Duration, and format of intervention contacts. Each of the 7 health CC education/coaching sessions by phone will last 15 to 20 minutes and will begin with participants being asked about their progress and their weight and informed of their weight change. At each visit, the participant and Lifestyle Coach (i.e., community health worker lifestyle change coach) will review the participant's completion of food and activity records since the previous visit. This will include examining an estimate of the number of daily calories consumed and minutes walked each week, as well as any other homework assignments assigned during the previous contact. The Lifestyle Coach will assist participants with problem solving and will then introduce the lesson from the DPP curriculum to be completed for the next visit. Participants will receive enough food

Patterned after protocol published online in association with Appel et al. (2011)¹⁵

monitoring records and activity records to last until their next visit. Participants will have until before their last follow-up assessment to complete all sessions. Visits that cannot be completed on-site (because of illness, travel, etc.) may be completed by phone. *Group health education* sessions will last 1 hour for the CC participants but will last 1 ½ hours for the MyP participants because the last ½ hour will consist of taste-testing fruit- and vegetable-rich recipes. Finally, the two in-home visits will last 50 minutes and will involve a discussion of strategies for keeping calorie intake low (DPP-like condition), for keeping fruit and vegetable intake high (MyP condition), and for maintaining a daily regimen of 30 minutes or more of moderate to vigorous physical activity (both conditions).

Dietary goals –CC condition: Participants in the CC condition will be prescribed a daily calorie goal based on body weight. Following recommendations from the Diabetes Prevention Program, persons who weigh \leq 114 kg (\leq 250 lb) will be prescribed 1200-1499 kcal/d and those $>$ 114 kg ($>$ 250 lb) 1500-1800 kcal/d. All participants will be encouraged to aim for the lower end of their range. DPP-like participants will be instructed to consume a diet of conventional table foods with $<$ 30% of calories from fat (including $<$ 10% from saturated fat), approximately 15%-20% of calories from protein, and the remainder from carbohydrate. This includes a goal of consuming 5 servings of fruits and vegetables, including juices, each day. Participants in this group will be provided a calorie guide (e.g., Calorie King) to use as they wish. In addition, participants will be informed of the caloric content of common food and food-products found at their home.

CC participants, for at least the first few weeks, will be asked to record all foods and beverages consumed for at least 3 days (2 weekdays and 1 weekend). This will begin at the first meeting with the Lifestyle Coach (at week 1). At the second meeting (Week 2), CC participants will be instructed to record their calorie intake with the assistance of the calorie guide provided (e.g., Calorie King). Food records will be reviewed at each meeting to determine participants' success in meeting calorie goals, and problem solving will be used to facilitate adherence. Over time, the effort required to monitor their daily energy intake is expected to diminish as participants automate their monitoring of the times, places, and activities associated with their eating. Although originally developed for use by middle class patients, interventions such as the ones described here can be adapted and made useful for low-literacy patients with guidance from community-savvy lifestyle change coaches.¹⁶⁴ The lifestyle change coach will also help participants develop an eating plan in which they consume breakfast, lunch, and dinner, with snacks as needed. Snacks will include fruits and vegetables to meet the goals described previously. Participants also will be provided meal plans (from the DPP) that suggest choices for breakfast, lunch, dinner, and snacks.

CC participants' calorie goals will be evaluated after the each health education session and adjusted appropriately based on an individual's desire to remain weight stable or lose more weight. This reduced schedule recognizes that even the most motivated participants tire of keeping daily records after the first 6 months.

Dietary goals –MyP condition: As was the case for CC participants, MyP participants will be encouraged to restrict calories but not through calorie counting but by making sure that half their typical plate is devoted to minimally processed fruits and vegetables, and that one quarter of their plate be grains, mostly whole grain, and that one quarter of their plate be protein-rich foods such as meat, fish, nuts and legumes. Because not every meal is on a plate, the MyP participants will be asked to consider every serving of grains and every serving of protein-rich food to be yoked to a prerequisite serving of fruit or a serving of vegetables. Having a serving of pizza is fine as long as it is accompanied by a serving of low-calorie salad or a serving of fruit (not juice). In addition to this recommendation, the participants will be asked to adhere to the other non-portion-control messages accompanying the MyPlate icon.¹⁶⁵ These messages include: "Switch to nonfat or low-fat milk," "Choose lower sodium foods," "Drink water instead of

Patterned after protocol published online in association with Appel et al. (2011)¹⁵

sugary drinks.” These messages represent complementary weight control strategies that are likely to facilitate desirable weight loss. Reducing discretionary fat is consistently recommended for weight loss^{20,25} and validated by the success of orlistat, a lipase inhibitor.^{166,167} While sodium is not itself caloric, its level in a food is reflective of how highly processed the food is. The consumption of high-salt, low-nutrient snack foods, in turn, has been associated with obesity risk.^{168,169} There is considerable consensus that sugary drink intake contributes to obesity^{160,170,171} and that replacing sugary intake with water would reduce risk.¹⁷²

Part of the challenge in trying suddenly to eat eight or more servings of F&V/day instead of the more usual four servings is that sensory-specific satiety will likely render larger quantities of fruit and vegetables increasingly unpalatable midway through a meal unless participants increase the variety and range of fruit and vegetable choices.¹⁶¹ Increasing the variety and range of fruit and vegetable choices will, in turn, run up against the typical human neophobic response to new plant foods. Part of the lifestyle coach’s challenge is to get the participant in the MyP condition to be willing to try a new food 8-14 times, because overcoming (permanently) the neophobic response to a specific plant food typically takes 8-14 exposures.⁶² The lifestyle coach will also suggest that a way to engender increased appetite for water-rich foods like fruits and vegetables is to exercise before the meal. In school children,¹⁷³ in athletes,^{74,174} and in overweight undergraduates¹⁶³ exercise before a meal increases appetite for water-rich foods. Conversely, fasting or skipping breakfast before a meal are associated with decreased appetite for F&V,^{162,175} so regularity of meal intake will be encouraged.

Another strategy for exposing participants to new plant foods in order to expand their repertoire of acceptable fruits and vegetables is to have the MyP participants take part in taste-testing dishes containing new plant foods. Vegetable-rich recipes will be solicited from study participants and submitted for review by the study Intervention Director. The recipes will be evaluated positively according to the quantity of the following dimensions: fruits and vegetables, minimally processed; whole grains; low-fat or non-fat dairy; lean proteins. The recipes will be evaluated negatively according to the quantity of the following: saturated fat; sodium; sugar. A score composed of the above dimensions will be used to rank order recipes. The ranking of recipe ingredients will favor selection of those recipes with the highest satiation/ highest satiety value for the fewest number of calories, thereby facilitating a program of weight loss featuring less hunger²⁰ and therefore greater likelihood of maintenance for the long-term.

